1.3.1 Rationale for trial endpoint and population

The primary endpoint of this trial offers a clear signal of efficacy as an undetectable PSA with non-castrate levels of testosterone at 24 months suggests no malignant tumor cells are producing PSA and hence are not active. This has been used in other clinical trials ([NCT02020070](#); [NCT01751451](#)) and offers an advantage over other interim endpoints such as PSA progression, radiographic PFS (e.g., time to metastatic disease), development of CRPC, or OS which can require a very lengthy follow up period in castration sensitive disease. An undetectable PSA in a subject who is post prostatectomy is a clear sign of the absence of cancer activity. Durability of an undetectable PSA in an environment rich with testosterone is synonymous with cure, and analogous to a complete response in solid tumors. Secondary endpoints, more synonymous with progression free survival (PFS) used in other immunotherapy trials, will also be collected and informative of the efficacy of this regimen.

This trial will include men who have had a radical prostatectomy and/or primary definitive radiation therapy to the prostate and have developed biochemical non-metastatic recurrence with a PSA doubling time placing them at high risk for metastases. This trial will allow those subjects who are ADT naïve, as well as those who have received intermittent ADT and currently are on an 'off cycle' of ADT. Allowance of subjects who have received a prior cycle of ADT and failed allows them to serve as their own control. In the biochemically recurrent "non-metastatic" population, the inability to identify gross metastatic disease is more a function of the limitations of conventional imaging (CT and

technetium bone scan) than it is a reflection of not having micro-metastatic recurrence. As novel tracers such as Prostate Specific Membrane Antigen (PSMA) PET imaging identifies disease earlier, and with greater sensitivity, a lead time bias is anticipated across trials. With more sensitive imaging, subjects with earlier metastatic disease may be enrolled in metastatic trials in the future. This trial will use conventional imaging with CT/MRI and bone scan to define non-metastatic disease. It will not exclude those subjects with disease only detectable using investigational PET imaging.

Moving into earlier disease states in the prostate cancer continuum is appealing as the immune system may be more receptive with fewer immunosuppressive cells and with less tumor burden to overcome. In clinical trials with prostate cancer, there have been hints that lower disease burden may be a more optimal setting for immunotherapy. Post hoc analysis of the IMPACT trial which evaluated the sipuleucel-T vaccine in mCRPC demonstrated that the subset of subjects with PSA values in the lowest quartile were more likely to benefit than those with PSA (as a very loose reflection of burden) in the highest quartile.⁵⁸ More recent data in melanoma using anti-PD1 antibodies suggests the ratio of reinvigorated exhausted T cells relative to tumor burden can be predictive of response to anti-PD1 therapy. The authors postulated that if the tumor burden is high, even a robust reinvigoration of T cells may not be enough.⁵⁹

Outside of the hypotheses generated for the timing of immunotherapy, there is growing evidence that utilization of chemotherapy, and more potent anti-androgens such as abiraterone previously only used in the castration resistant setting can have a more profound impact when used in castration sensitive disease relative to ADT alone. The use of ADT with docetaxel for 6 cycles in metastatic castration sensitive prostate cancer as compared to ADT alone as well as abiraterone with prednisone with ADT relative to ADT alone in the castration sensitive (non-castrate) metastatic disease setting are now supported by several large phase III trials.⁶⁰ The CHAARTED trial found the greatest benefit in those deemed to have a higher 'burden' of metastatic disease and the LATITUDE trial required at least 3 bone metastases.⁶⁰⁻⁶² Where subjects with minimal metastatic disease (e.g., 1-2 bone metastases, or low volume unresectable nodal disease) are best served is not altogether clear.

1.3.2 *Hypothesis*

PARP inhibition in subjects with prostate cancer harboring HRR mutations will reduce tumor burden and cause apoptosis of the cell, leading to neoantigen release, activation of the cyclic GMP-AMP synthase (cGAS)-Stimulator of Interferon Genes (STING) pathway, which in combination with PDL1 blockade may lead to durable responses. This combination may be effective in treating recurrent prostate cancer without the use of ADT, a maneuver which is associated with only temporary response, an inability to cure, and significant quality of life detriment. For those who do not achieve an undetectable PSA with normal testosterone at 4 months, ADT for a fixed course will be added starting the following cycle to determine if they can be "salvaged" with triplet therapy, as ADT has been demonstrated to increase cytotoxic T cell proliferation and will reduce tumor burden.

2. OBJECTIVES

2.1 Primary Objective

To assess the therapeutic efficacy as defined by an undetectable PSA (<0.05 or PSA <0.10 for institutions where this is the lower limit of detection) with non-castrate levels of testosterone using the combination olaparib (PARP inhibition) with durvalumab (PDL1 inhibition) at 24 months (cycle 24) in biochemically recurrent prostate cancer.

2.2 Secondary Objectives

- To determine if a non-castrating regimen can provide disease control as measured by an undetectable PSA (without ADT) at 5 months (cycle 5).
- To evaluate the safety of the combination of olaparib and durvalumab

2.3 Exploratory Objectives

To determine:

- Undetectable PSA at 11 months (cycle 11) (irrespective of testosterone level)
- Time to PSA progression defined as the time to PSA increase that is $\geq 25\%$ and $\geq 2\text{ng/mL}$ above the nadir, and which is confirmed by a second value > 3 weeks later
- Change in PSA doubling time at 24 months relative to PSA doubling time from the first dose of study drug (using the last 3 values from each time point)
- Comparison of Patient Reported Outcome (PRO) assessments of toxicity (PRO-CTCAE) to clinician reported toxicity assessments (CTCAE v.5.0)
- Changes in immune biomarkers with treatment. Peripheral blood mononuclear cells (PBMCs) will be collected that can later be analyzed for the immunomodulatory effects of the regimen by measuring for example, discrete T-cell populations. Archival tissue will also be analyzed for immune-related genes that may associate with response.

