3.1.2 Males 18 years of age and above

3.1.3 Body weight $> 30\text{kg}$

3.1.4 History of radical prostatectomy and/or primary radiation therapy to the prostate

3.1.5 Histologically confirmed prostate cancer with progressive disease defined as:

- Rising PSA (50% or more increase to a level of 0.50 ng/mL or more, based on at least 3 PSA determinations obtained at least 1 week apart). The 50% rise in PSA is across the 3 determinations, and these determinations do not need to be sequential.
- PSA doubling time of \leq 9months as calculated according to the Memorial Sloan Kettering Cancer Center nomogram
(<http://www.mskcc.org/mskcc/html/10088.cfm>)

3.1.6 No evidence of metastatic disease on conventional imaging (CT/MRI and bone scan). However, subjects with pelvic and/or retroperitoneal nodes $< 2\text{cm}$ in the short axis will be permitted on study, as they are considered not to have definitive metastases. (Note: *Metastatic disease on investigational imaging, Prostate Specific Membrane Antigen-targeted (PSMA) PET, PET-choline, or other novel PET tracers who do not have evidence of metastatic disease using conventional imaging (CT/MRI, bone scan) are allowed.*)

3.1.7 Molecular evidence of DDR deleterious mutations (somatic or germline), including BRCA1, BRCA2, ATM, CHEK1, CHEK2, FANCA, RAD51B, RAD51C, RAD51D, RAD54L, PALB2, BRIP1, BARD1, or CDK12. Mutations may be truncating, splice site mutations, missense or homozygous deletions. Mutation status is determined by a local laboratory with the result documented in the subject's medical record, previously obtained genomic testing from a CLIA-certified lab, or via archival or fresh tissue.

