8. CRITERIA FOR OUTCOME ASSESSMENT/THERAPEUTIC RESPONSE

8.1 Therapeutic Response

8.1.1 PSA

This trial will measure PSA monthly for the first 24 months. The primary endpoint is an undetectable PSA at 24 months with non-castrate levels of testosterone (>150 ng/dL).

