10.5 Statistical Procedures and Analysis

Summary statistics include the number of observations, mean, standard deviation, median, minimum, and maximum values.

Statistical methods for the analyses

An exact binomial test will be used to evaluate the efficacy of the 24 months undetectable PSA endpoint. In addition, the proportion of subjects that attain an undetectable PSA at (1) 5 months, (2) 11 months, and (3) 24 months will be computed along with their attendant 95% confidence intervals. The probability of PSA progression over time will be estimated using the cumulative incidence function.

A paired t-test will be used to compare the PSA doubling time at 24 months to the PSA doubling time at study entry.

Kendall's tau with longitudinal data will be used to compare patient recorded toxicities to physician recorded toxicities over time.

The immunologic profile of patients over time will be described using nonparametric kernel smoothing.

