APPENDIX B: STUDY CALENDAR

(A cycle = 28 days; a month = 28 days)

	Screening		Treatment/Intervention Period									End of Treatment (EOT) within 30 days of last dose	Follow Up ^s	
			Cycle 1		Cycle 2		Cycle 3	Cycle 4	Cycle 5	Cycle 6	Cycle 7- Cycle 24			
	Day -42 to Day -1	Day -14 to Day -1	Day 1 (± 3 d)	Day 15, (± 3 d)	Day 1 (± 3 d)	Day 15 (± 3 d)	Day 1 (± 3 d)	(± 7 d)						
Informed consent and research authorization/ HIPAA form ^a	X													
Demographics, medical history, histologic confirmation	X													
Physical examination, Vitals (Blood Pressure, Pulse, Temperature), weight ^b	X		X	X	X	X	X	X	X	X	X	X	X	
Height	X													
12-lead EKG	X													

Olaparib + Durvalumab
Memorial Sloan Kettering Cancer Center

c17-192

	Screening		Treatment/Intervention Period								End of Treatment (EOT) within 30 days of last dose	Follow Up ^s
			Cycle 1		Cycle 2		Cycle 3	Cycle 4	Cycle 5	Cycle 6		
	Day -42 to Day -1	Day -14 to Day -1	Day 1 (± 3 d)	Day 15, (± 3 d)	Day 1 (± 3 d)	Day 15 (± 3 d)	Day 1 (± 3 d)	(± 7 d)				
Performance status	X		X	X	X	X	X	X	X	X	X	X
Concomitant medications	X		X	X	X	X	X	X	X	X	X	X
Adverse Events	X		X	X	X	X	X	X	X	X	X	X
Radiologic evaluations and measurements ^c	X		For non-metastatic, rising PSA subjects, radiologic tests are performed at Cycle 5 (+/- 2 week), Cycle 24 (+/- 2 week) or at EOT (+/- 2 week) if discontinued sooner.								X ^d	
CBC w/ diff plts ^e		X	X	X	X	X	X	X	X	X	X	X
Comprehensive Metabolic Panel ^f		X	X	X	X	X	X	X	X	X	X	X
Coagulation Tests ^g		X										
PSA ^h		X	X		X		X	X	X	X	X	X
TFTs ⁱ		X			X			X		X	X	X
Testosterone ^j		X								X	X	
Hepatitis Panel		X										
HIV		X										
Urinalysis ^k		X										

Olaparib + Durvalumab
Memorial Sloan Kettering Cancer Center

c17-192

	Screening		Treatment/Intervention Period								End of Treatment (EOT) within 30 days of last dose	Follow Up ^s
			Cycle 1		Cycle 2		Cycle 3	Cycle 4	Cycle 5	Cycle 6		
	Day -42 to Day -1	Day -14 to Day -1	Day 1 (± 3 d)	Day 15, (± 3 d)	Day 1 (± 3 d)	Day 15 (± 3 d)	Day 1 (± 3 d)	(± 7 d)				
PBMC ^t		X		X					X		X	X
PRO-CTCAE ^m	X								X		X	X
cfDNA ⁿ		X							X			X
PDL-1 Expression (archived tissue) ^o	X											
Tissue Sequencing ^p	X											
Normal Sample ^q	X											
Olaparib Administration ^r								X				
Durvalumab Administration ^r								X				
ADT Administration ^r								X				

- a. Informed consent and radiologic assessments should be obtained within 42 days.

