- b. Refer to section 6.1 for monitoring of vital signs and observation period.

Olaparib + Durvalumab
Memorial Sloan Kettering Cancer Center

c17-192

- c. Radiographic evaluations will include CT CAP with contrast or MRI with contrast of the abdomen and pelvis, and CT chest without contrast. Radionuclide bone scan will be performed. All disease sites must be assessed using the same methodology as performed at baseline. At the discretion of the investigator, additional radiological evaluations may be performed at an unscheduled time point.
- d. If radiographic evaluations were completed within 30 days of EOT, they do not need to be repeated.
- e. CBC w/diff, platelets will be monitored biweekly during Cycle 1 and 2, and monthly from Cycle 3-Cycle 24 (see section 5.1.9 for additional information regarding laboratory tests)
- f. CMP will be monitored biweekly during Cycle 1 and 2, and monthly from Cycle 3-Cycle 24 (see section 5.1.9 for additional information regarding laboratory tests)
- g. APTT and INR. See section 5.1.9 for more information on coagulation tests.
- h. PSA will be collected monthly during each cycle.
- i. Thyroid function tests (TFTs), including TSH, free T4, and free T3 will be monitored every other cycle (beginning with Cycle 2, Cycle 4, Cycle 6, etc.)
- j. Testosterone will be monitored at Screening, Cycle 6, Cycle 11 and every other month from Cycle 12-Cycle 24
- k. Urinalysis: to be collected at screening. If clinically indicated, urinalysis should be performed while on treatment. See section 5.1.9 for additional information.
- l. Peripheral Blood Mononuclear Cells (PBMCs) will be drawn C1D1 before treatment, Cycle 2, Cycle 5, Cycle 11, and EOT.
- m. QoL Assessment (PRO-CTCAE) compared from screening, Cycle 5, Cycle 11, and EOT.
- n. Non-immune blood biomarkers: cfDNA from C1D1 before treatment, Cycle 5, and EOT.
- o. Tissue biomarkers: PDL1 expression at screening.
- p. Tissue sequencing does not need to be repeated if performed prior to consent and subject has a confirmed DDR mutation. If DDR mutation status is unknown or sequencing was not previously performed, archival tissue as well as a matched normal sample must be sent for Next Generation Sequencing. If available, additional archival tissue from all subjects should be sent and banked for future analysis of immune markers.

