- q. A blood or saliva sample will be collected during screening as matched normal for sequencing for patients completing prospective Next Generation Sequencing using assays that require a matched normal sample.
- r. Subjects will be treated concurrently with olaparib + durvalumab continuously for 24 months. Durvalumab will be administered on Day 1 of each cycle (± 3). After the first 4 months, if a subject fails to achieve an undetectable PSA [PSA of <0.05 (or PSA <0.10 for institutions where this is the lower limit of detection) with the combination of olaparib and durvalumab, ADT will be added for 6 months (starting at Cycle 5) while continuing treatment with olaparib and durvalumab (see section 6.3 for additional details regarding ADT). For subjects who have an undetectable PSA after the first 4 months of treatment, they will continue on the combination of olaparib + durvalumab continuously for 24 months (without ADT). As long as it is believed that subjects are clinically benefiting, they will remain on treatment for up to 24 months with olaparib and durvalumab. For example, a subject with a PSA reduction that does not achieve an undetectable PSA would be allowed to remain on study for the duration of the trial. Subjects who meet progression criteria while on active therapy would come off of trial.
- s. Subjects who have an undetectable PSA after completion of protocol therapy will be followed every 12 weeks. PSA, CMP, CBC, and TFTs should be performed. A physical exam will be performed. Subjects who respond and later progress in the first year following the 24 month treatment phase will be allowed to re-induce with the combination and will restart their calendar with C1D1 if they continue to meet all clinical eligibility criteria are met. PCCTC must review the confirmation of eligibility prior to re-inducing treatment.

APPENDIX C. ACTIONS REQUIRED IN CASES OF COMBINED INCREASE OF AMINOTRANSFERASE AND TOTAL BILIRUBIN – HY'S LAW

Introduction

This Appendix describes the process to be followed in order to identify and appropriately report cases of Hy's Law. It is not intended to be a comprehensive guide to the management of elevated liver biochemistries. Specific guidance on the managing liver abnormalities can be found in Appendix H and Appendix I of the protocol.

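### The exploratory month-24 PSA doubling time rests on three monthly values over 56 days and is tested on the month scale; a longer window and a slope-scale test would make it far more informative at little cost

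*Combined protocol and SAP*

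**What the plan says.** Section 2.3 lists the change in PSA doubling time at 24 months as an exploratory objective and limits each estimate to three measurements: "using the last 3 values from each time point". Section 10.5 gives the analysis: "A paired t-test will be used to compare the PSA doubling time at 24 months to the PSA doubling time at study entry". Neither section states a fitting method, a minimum time span, a transformation, or how to handle a flat, falling or undetectable PSA.

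Appendix B (footnote h) states that "PSA will be collected monthly during each cycle", and section 8.1.1 agrees: "This trial will measure PSA monthly for the first 24 months". The calendar also defines its unit: "A cycle = 28 days; a month = 28 days". Section 2.1 equates 24 months with Cycle 24.

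At entry, criterion 3.1.5 requires a doubling time of at most 9 months and a PSA rise "based on at least 3 PSA determinations obtained at least 1 week apart". Three such values could therefore span as little as 14 days, or much longer.

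**The concern.** The analysis looks for men whose PSA is still detectable but rising more slowly than before. The protocol allows such men to reach Cycle 24: section 5 keeps on treatment a man whose PSA falls without becoming undetectable, and section 5.7 requires a confirmed rise of at least 25% and 2 ng/mL before removal for PSA progression.

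A slow rise is the hardest to measure over a short span. The last three monthly values cover 8 weeks, although monthly PSAs over a much longer period are already scheduled. Doubling time is also ln 2 divided by the slope, so a slope estimated near zero gives a huge doubling time, and one just below zero gives a huge negative one. A few such men can dominate a paired t-test on months. A null result would then not distinguish no slowing from measurement noise.

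**Working it through.** **The plan's own figures.** No precision or power is stated for this analysis. The only stated design figures concern the primary endpoint (32 subjects, 8 or more successes, size 0.10 at 0.15, power above 0.90 at 0.35). Exact binomial calculation gives size 0.0958 and power 0.918, so they reproduce. They do not depend on the point below.

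**Inputs from the documents.** Three values, 28 days apart: span 2 × 28 = 56 days. Entry doubling time at most 9 months.

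**Assumed inputs (not in the documents).** Within-man PSA CV of 5%, 10% or 15%; a true month-24 doubling time of 9 months; and, for power, a true lengthening from 6 to 9 months, 16 evaluable men, three entry values over 3 months, between-man SD of 0.3 on the log scale, and two-sided 0.05.

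**Step 1: size of the signal.** At a 9-month doubling time PSA rises by 2^(56/(30.44 × 9)) − 1 = 15% over 56 days in calendar months. With the calendar's 28-day month it is 2^(2/9) − 1 = 17%.

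**Step 2: precision with three values.** True slope = ln 2/9 = 0.0770 per month. SE(slope) = CV/√Σ(t − t̄)². With spacing 28/30.44 = 0.92 months, Σ = 2 × 0.92² = 1.69 and its root is 1.30.

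| CV | SE(slope) | SE as % of slope | Chance slope estimate is negative |
|---|---|---|---|
| 5% | 0.0384 | 50% | 2% |
| 10% | 0.0769 | 100% | 16% |
| 15% | 0.1153 | 150% | 25% |

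The last column is Φ(−slope/SE). With 28-day months the root is √2 = 1.41 and the ratios become 46%, 92% and 138%, so the conclusion does not depend on the convention.

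**Step 3: precision with more of the scheduled values.** In units of one visit interval, Σ is 2 for three values, 10 for five and 28 for seven (Cycles 18 to 24). Seven values cut the SE by √(28/2) = 3.7, to 13%, 27% and 40% of the slope. Five cut it by √(10/2) = 2.2, to 22%, 45% and 67%. These reduction factors depend only on the visit schedule, not on the assumed CV.

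**Step 4: power of the paired comparison, by simulation** (repeat runs agree to about one percentage point).

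| Month-24 values | Test scale | CV 5% | CV 10% |
|---|---|---|---|
| 3 (as planned) | months | 27% | 1% |
| 7 | months | 88% | 30% |
| 3 | slope | 90% | 39% |
| 7 | slope | not tabulated | 82% |

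**Step 5: the entry side.** In a separate setting (true doubling of the doubling time, 20 men, CV 10%, months scale), seven month-24 values give power 0.90 if the entry doubling time is well measured, but only 0.45 if it rests on three values over 56 days. Lengthening only the month-24 window is therefore a partial repair.

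**The case against.** The strongest objection is that the window is not the main culprit. A reader might infer that 56 days is simply too short to measure doubling times of 6 months or more, and that this alone defeats the test. The documents do not support that. They give no PSA variability, and at CV 5% the 95% interval for a true 6-month doubling time (28-day months) is 3.8 to 15 months: wide, but bounded. Changing only the scale, with the planned three values, matches or exceeds changing only the window. This part of the objection stands, and it is why the remedy needs both changes.

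Part of the loss also reflects the missing rule for non-positive slopes. Dropping those men raises planned power to about 46% at CV 5% and 8% at CV 10%. That stands too, although at CV 10% it rescues little.

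Seven usable values are not assured. Men without an undetectable PSA receive ADT for 6 months from Cycle 5, three-month formulations are allowed (section 6.3), and testosterone is checked only every other month from Cycle 12. Recovery will be dated coarsely, and PSA need not be log-linear while testosterone is recovering. The 3.7-fold gain is thus a best case; with five values on the months scale, power at CV 10% is only 16%.

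The number of evaluable men is also unknown, since men with undetectable PSA have no doubling time and men removed for progression have no month-24 value. Finally, a reader might infer that unequal precision at entry and month 24 invalidates the paired t-test. It does not: the test uses within-man differences, and imprecision on either side costs power.

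**Conclusion.** The point holds as a low-severity improvement. The three-value rule, the 56-day span and the months-scale test are in the text, and the 3.7-fold gain from seven values follows from the schedule alone. How imprecise the planned estimate is depends on the assumed CV. The power figures also depend on the assumed 16 men, the 6-to-9-month lengthening and the entry sampling, so they illustrate the comparison and do not forecast the trial's power. Under those assumptions, window and scale each contribute to the loss, and correcting either alone leaves power at 30 to 39% at CV 10%. The endpoint is exploratory, with no stated alpha or power and no decision rule attached, so the trial's main conclusion is not at risk.

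**What to change.** In sections 2.3 and 10.5:

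- At month 24, regress log PSA on actual draw date, using all detectable monthly values from Cycle 18 to Cycle 24 drawn after documented testosterone recovery. Require at least three values, and report how many each man contributes.
- At entry, use all available post-therapy values with their actual dates.
- Make the paired comparison on the log-PSA slope (ln 2/doubling time), and report doubling times descriptively.
- Keep the three-value version as a sensitivity analysis.

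The cost is a wording change: the on-study PSAs and testosterone checks are already scheduled, and no visit is added. The trade-off is that growth is assumed log-linear over up to 24 weeks instead of 8, which is why the restriction to values after testosterone recovery matters.
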